### **3.1.3. Demographics**

Baseline demographic data and sleep history will be summarised for each analysis set

The following will be summarised:

#### Demography

- Age
- Gender (Male/Female)
- Height
- Weight
- BMI categorised as:
  - 18.5 or less = Underweight
  - 18.5 to 24.9 = Normal Weight
  - 25.0 to 29.9 = Overweight
  - 30.0 to 39.9 = Obese
  - 40 and above = Morbidly Obese
- Ethnicity(White, Mixed/multiple ethnic backgrounds, Asian/Asian British, Black/ African/ Black British, Other)
- Marital status (Married or living with partner, Single, Separated or divorced, Widowed, Rather not say)
- Education level (Primary school, Secondary school, College, University)
- Employment status (Full-time work, Part-time work, Unemployed, Retired, Student)
- Breast feeding (Y/N)
- Menopausal status (Pre-menopause, Peri-menopause, Post-menopause, Don't know)
- Shift work (Y/N)

#### Sleep history

- Sleep difficulties (Y/N)
- Started/worsened since diagnosis of breast cancer (Y/N)
- Medications prescribed by doctor for sleep issues (Y/N)
- Sleep apnoea (Y/N)
- Access to smartphone (Y/N)

### **3.1.4. Medical History of Breast Cancer**

The following will be summarized for the stage 2 analysis set only.

- Time since breast cancer diagnosis (derived as consent date-diagnosis date+1)
- Stage of disease (Stage I to Stage III)
- Tumor staging (T1, T2, T3, T4, DCIS)
- Nodes staging (N0, N1, N2, N3)
- Surgery type (Lumpectomy, Mastectomy, Double Mastectomy, No surgery, Not available)

Statistical Analysis Plan for CLM-INS-004

Version: Final 2.0

Date: 9th September 2022

- Time since surgery (derived as consent date-surgery date+1, for applicable patients)
- Neoadjuvant treatment (Y/N)
- Oestrogen receptors (Y/N)
- Progesterone receptors (Y/N)
- HER2 receptors (Y/N)

### **3.1.5. Breast Cancer treatments**

Previous and current Breast cancer treatment will be summarized for the stage 2 analysis set only based on the following:

- Current systemic anti-cancer therapy
- Time since start of current systemic anti-cancer therapy
- Number of cycles of current systemic anti-cancer therapy
- Dexamethasone treatment (Y/N)
- Time since start of dexamethasone treatment (for applicable patients)
- Radiation therapy? (Y/N)
- Time since start of radiation therapy
- Hormonal treatment? (Y/N)
- Current hormonal treatment (for applicable patients)
- Time since start of hormonal treatment (for applicable patients)
- Targeted therapy for HER2 positive breast cancer? (Y/N)
- Current targeted therapy (for applicable patients)
- Time since start of targeted therapy (for applicable patients)

### **3.1.6. Co-morbidities**

Any co-morbidities will be summarised for the stage 2 analysis set only based on the number and % of patients with any of the following conditions and the number and % of patients receiving medication for each relevant condition:

- Cardiovascular disease
- Chronic pulmonary disease (not asthma)
- Asthma
- Chronic kidney disease
- Gastrointestinal disease
- Genitourinary disorder
- Liver disease
- Chronic neurological disorder
- Psychiatric disorder
- Chronic hematologic disease
- Rheumatologic disorder
- Immunological disorder
- Endocrine (including diabetes) disorder

Statistical Analysis Plan for CLM-INS-004

Version: Final 2.0

Date: 9th September 2022

- Musculo-skeletal disorder
- Other

### **3.2. Questionnaire data**

#### **3.2.1. ISI**

The primary outcome of Stage 1, the prevalence estimate for insomnia in the breast cancer cohort studied, will be reported as the number and percentage of patients in the Stage 1 analysis set determined as having insomnia by the ISI assessment. Insomnia will be defined as a total score of 8 or more. Exact Clopper-Pearson 95% confidence intervals for the prevalence rates will also be reported.

Note, if any patients in the stage 1 analysis set do not have evaluable ISI data (i.e., total score) then the prevalence rate and 95% confidence interval will also be derived based on evaluable patients only.

Insomnia severity will be assessed by calculating the number and percentage of participants within each of the ISI categories:

- no clinically significant insomnia (ISI score 0-7)
- subthreshold insomnia, (ISI score 8-14)
- clinical insomnia of moderate severity (ISI score 15-21)
- severe clinical insomnia (ISI score 22-28).
- missing (if applicable)

For Stage 2, severity categories will be summarized at baseline and day 21 and a shift table will also be presented to show any change in severity since baseline.

Severity categories will also be graphically displayed in the form of bar charts for the relevant timepoints for each stage.

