7.3.3 Questionnaire Completion

Following completion of patient registration into the eCRF, the electronic Patient Reported Outcomes (ePRO) module of the eCRF will be activated to send a text message (or email, if required) containing a link to the baseline questionnaire set to consenting participants. This questionnaire set consists of five short questionnaires including:

- Insomnia Severity Index: ISI
- Quality of life: EQ-5D-5L and FACT-ES
- Demographics and sleep history: age, gender, weight, height, ethnicity, marital status, educational level, current occupation, pregnancy, breastfeeding, menopausal status, shift-work/night-work and smartphone access. Sleep-related questions to determine if the patient has experienced sleep disturbance prior to the screening/baseline consultation with beginning or worsening of sleep disturbance since breast cancer diagnosis and if patient has suffered or currently suffering from sleep apnoea.

The participant can complete the questionnaires on their smartphone. It is estimated the participant will take 20-25 minutes to complete these questionnaires. If the participant does not complete the baseline questionnaire within 3 days, the eCRF will send a questionnaire reminder text message (or email, if required). This will be repeated on two subsequent occasions if the questionnaire remains uncompleted for the three preceding days. The eCRF can be configured to notify the clinical study team by email when a participant completes the questionnaire set. Questionnaires can also be completed on computer or tablet however smartphone completion is preferred.

The baseline questionnaire set can be completed on paper if the clinic, however clinic study staff will be required to subsequently enter the data recorded by the participant directly into eCRF.

7.4 Stage 2

Briefly, Stage 2 will run separately from Stage 1 to aid the timely recruitment and flow of participants through the study. Participants will be asked to consent to taking part in Stage 2, separately from the consent to take part in Stage 1. As participants in Stage 1 will have consented to the use of their contact details for the purposes of being invited to take part in Stage 2, all recruitment and procedures in Stage 2 will be carried out remotely. Figure 3 describes Stage 2 procedures.

[figure not shown]

Figure 3. Outline of Stage 2 study procedures.

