7.4.1 Stage 2 Eligibility Assessment

All questionnaire-derived eligibility-related data for each participant will be present within the eCRF. This will enable the clinical study team to populate the eligibility eCRF including ISI scores and data related to self-reported sleep history, sleep apnoea, shift-work or night-work, possession of smartphone and breast feeding. The EDC will be configured to automatically calculate the total ISI score required for assessment of eligibility to Stage 2. The clinical research team will be required to confirm from patient medical records the stage of breast cancer, any other diagnosis of cancer, not including basal cell carcinoma of the skin or cervical carcinoma in situ, within the previous 5 years, and any comorbidities incompatible with study participation.

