10 STATISTICS AND DATA ANALYSIS

10.1 Sample size calculation

The sample size required for Stage 1 is based on an assumed prevalence of insomnia of 44% in breast cancer patients (midway point of insomnia prevalence range found in breast cancer patients 19-69%)⁴⁻¹⁰. A sample size of 267 participants is required for estimating the expected prevalence rate with 5% absolute precision and 90% confidence or 6% absolute precision and 95% confidence²⁹.

The target for Stage 2 is for approximately 100 participants to complete the study, to provide sufficient data to assess the secondary objectives. With an assumed prevalence of 44% and a 20% drop out rate, then 285 participants in Stage 1 would give an expected 125 eligible participants for Stage 2 with 100 participants assumed to complete the 3-week observation period.

Therefore, the study will aim to recruit a minimum of 285 patients into Stage 1 to cover the sample size requirements for Stage 1 and Stage 2.

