### 2.2. Definitions of Analysis Sets

The following analysis sets will be used in the statistical analyses and reporting of study data.

- Stage 1 analysis set will include all participants who consented to stage 1, are eligible for the study and have evaluable data for at least one of the questionnaires (ISI, EQ-5D-5L or FACT-ES).
- Stage 2 analysis set will be a subset of the Stage 1 analysis set and will include eligible Stage 1 participants who scored  $\geq 8$  on their baseline ISI questionnaire and consented to stage 2. Note if a patient consents to Stage 2 but does not provide **any** stage 2 data (e.g., questionnaire/sleep data) then they will be excluded from the stage 2 analysis set.

Statistical Analysis Plan for CLM-INS-004

Version: Final 2.0

Date: 9th September 2022

Note, listings will generally be based on the stage 1 analysis set with an indicator for patients who also entered into stage 2, with the exception of the cancer history, cancer treatment, co-morbidities, sleep diary, AE and UEQ listings which will be based on the stage 2 analysis set since these are only completed for stage 2 patients.

If a participant does not enroll in the digital diary (i.e., does not even download the app) but completes the UEQ, then data from the UEQ will not be included in the reporting of the data.

Percentages will generally be derived based on the analysis set N as the denominator, unless stated otherwise. Where there is missing data, % may be derived based on those within the analysis set who have evaluable data. Where applicable missing categories will be included to show the number of patients with missing data for the relevant endpoint.

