### **2.5. Missing Data Handling Rules**

In general, other than for partial dates, missing data will not be imputed and will be treated as missing. Where applicable, outcomes may still be derived for questionnaire data based

Statistical Analysis Plan for CLM-INS-004

Version: Final 2.0

Date: 9th September 2022

on missing data rules. For example, FACT scores can still be derived provided <50% of data is missing. Any missing data rules are provided in the relevant derivation sections.

Where applicable missing categories will be presented to show the number of patients with missing data for the relevant endpoint.

Imputation of partial dates

*Initial diagnosis date:*

- If year is missing, do not impute.
- If only day is missing, impute day as 15th of the month.
- If day and month are missing, impute as July 1st.

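### The primary prevalence divides by the whole Stage 1 analysis set, so a participant without an ISI total counts in effect as having no insomnia; the planned evaluable-only figure should be primary

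*SAP*

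**What the plan says.** SAP 3.2.1 ties the primary outcome to the full Stage 1 set: the prevalence "will be reported as the number and percentage of patients in the Stage 1 analysis set determined as having insomnia by the ISI assessment", where insomnia is a total of 8 or more, with an exact Clopper-Pearson 95% interval. If some patients in the set lack an ISI total, "then the prevalence rate and 95% confidence interval will also be derived based on evaluable patients only". The severity table in the same section has its own row for missing data.

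SAP 2.2 defines the Stage 1 set as consenting, eligible participants who "have evaluable data for at least one of the questionnaires (ISI, EQ-5D-5L or FACT-ES"). An ISI total is therefore not required. The same section sets the default denominator: "Percentages will generally be derived based on the analysis set N as the denominator, unless stated otherwise". It then permits, without requiring, an evaluable-only denominator where data are missing.

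SAP 2.5 says that in general "missing data will not be imputed and will be treated as missing", apart from partial dates and any rules given in the derivation sections. No such rule is given for the ISI.

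Protocol 3.3 and 10.3.2 express the primary outcome as a proportion of screened Stage 1 patients and do not say how to handle a missing ISI.

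**The concern.** A Stage 1 participant with an evaluable EQ-5D-5L or FACT-ES but no ISI total stays in the denominator of the primary proportion and cannot enter the numerator. No rule says that a missing ISI means no insomnia, but the arithmetic has that effect, and it sits badly with the general rule that missing values are treated as missing.

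Estimating this proportion is the study's primary objective. If missingness is unrelated to insomnia, the headline figure equals the evaluable-only figure multiplied by (1 − missing fraction), and its confidence interval moves down with it. The full-set figure is not labelled as a lower bound, and no corresponding upper bound is planned, so a reader who takes the primary result at face value gets an interval that leans one way.

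**Working it through.** **Inputs.** Assumed prevalence 44%, a Stage 1 requirement of 267 and a recruitment target of 285 (Protocol 10.1, SAP 1.2.1). Planned precision: "5% absolute precision and 90% confidence or 6% absolute precision and 95% confidence". The documents give no missing-ISI rate, so the numbers missing below are assumptions.

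**The plan's own figure.** With n = z²p(1−p)/d²:
- 5 points, 90% confidence: 1.645² × 0.44 × 0.56 / 0.05² = 266.7, so 267.
- 6 points, 95% confidence: 1.96² × 0.44 × 0.56 / 0.06² = 262.9, so 263, which 267 covers.

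The stated 267 reproduces. A target of 285 leaves 285 − 267 = 18 participants who could lack an ISI total before the evaluable number falls below the requirement.

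**Two estimates.** Let N = 285, m the number without an ISI total, and x = round(0.44 × (N − m)) the observed cases. The full-set estimate is x/N, the evaluable-only estimate is x/(N − m), and the upper bound that counts every missing patient as a case is (x + m)/N. Intervals are Clopper-Pearson 95%. Coverage is by exact binomial enumeration at a true prevalence of 44%, with missingness unrelated to insomnia.

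| Missing | Full set (95% CI) | Evaluable only (95% CI) | Upper bound | Coverage, full set | Coverage, evaluable only |
|---|---|---|---|---|---|
| 0 | 125/285 = 43.9% (38.0–49.8) | same | 43.9% | 0.958 | 0.958 |
| 3 (1%) | 124/285 = 43.5% (37.7–49.5) | 124/282 = 44.0% (38.1–50.0) | 44.6% | 0.956 | 0.952 |
| 6 (2%) | 123/285 = 43.2% (37.3–49.1) | 123/279 = 44.1% (38.2–50.1) | 45.3% | 0.949 | 0.954 |
| 14 (5%) | 119/285 = 41.8% (36.0–47.7) | 119/271 = 43.9% (37.9–50.0) | 46.7% | 0.904 | 0.957 |
| 18 (6.3%) | 117/285 = 41.1% (35.3–47.0) | 117/267 = 43.8% (37.8–50.0) | 47.4% | 0.865 | 0.952 |
| 28 (10%, stress case) | 113/285 = 39.6% (33.9–45.6) | 113/257 = 44.0% (37.8–50.3) | 49.5% | 0.717 | 0.956 |

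The gap between the two estimates is under 1 point up to 2% missing and 2.2 points at 5%, about a third of the planned 6-point precision (2.2/6 = 0.37).

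**If missingness is related to insomnia.** Let p be the prevalence in evaluable patients and q that in patients without an ISI total. The prevalence in the whole set is [(N − m)p + mq]/N. Against that target:
- bias of the full-set figure = −(m/N)q
- bias of the evaluable-only figure = (m/N)(p − q)

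The full-set figure is therefore the closer one only if q < p/2, which is 22% when p = 44%. At 14 missing:

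| q | Bias, full set | Bias, evaluable only | Coverage, full set | Coverage, evaluable only |
|---|---|---|---|---|
| 0% | 0.0 | +2.2 | 0.963 | 0.891 |
| 22% | −1.1 | +1.1 | 0.947 | 0.940 |
| 44% | −2.2 | 0.0 | 0.904 | 0.957 |
| 66% | −3.2 | −1.1 | 0.827 | 0.945 |

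Bias is in percentage points.

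**The case against.** The strongest reply is that SAP 3.2.1 already deals with most of this. The evaluable-only prevalence and interval are mandatory once any ISI total is missing, and the severity table counts the missing separately. A reader would see both figures and the number missing. That stands: what remains is which figure is primary and how each is labelled.

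Second, missing ISI totals may be rare. The questionnaires go out as one set with a first reminder, and "This will be repeated on two subsequent occasions if the questionnaire remains uncompleted for the three preceding days" (Protocol 7.3.3). Protocol 7.4.1 adds that "The EDC will be configured to automatically calculate the total ISI score required for assessment of eligibility to Stage 2". Anyone with no evaluable questionnaire is outside the set altogether. This also stands, and makes the upper rows of the first table the more likely ones.

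Third, evaluable-only is not always better. The ISI wording in Protocol Appendix 16.1 refers to the respondent's sleep problem, so good sleepers might be the ones who leave items blank. If prevalence among the missing is below half the evaluable rate, the full-set figure is closer. Nothing in the documents settles this. It is a reason to report both bounds, but not to make the figure at one extreme the primary one.

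Fourth, the protocol's denominator of screened patients may look closer to the full set. It can equally be read as those who completed the ISI, and it gives no instruction to count a missing ISI as a non-case.

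**Conclusion.** The concern holds, as a minor point. As written, the primary estimate can only match or understate the prevalence in the Stage 1 set, and its interval loses its nominal level as ISI totals go missing: coverage is 0.949 at 2% missing and 0.904 at 5%, while the evaluable-only interval stays between 0.952 and 0.958. These figures assume N = 285, 44% prevalence and missingness unrelated to insomnia; the missing rates are assumptions too. The effect is zero if every Stage 1 participant has an ISI total. No hypothesis test or decision threshold rests on the figure.

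**What to change.** In SAP 3.2.1:
- Define the primary estimate as participants with an ISI total of 8 or more divided by Stage 1 participants with an evaluable ISI total, with its Clopper-Pearson interval and the number missing beside it.
- Keep the full-set figure, relabelled as a lower-bound sensitivity analysis (every missing ISI taken as no insomnia).
- Add the matching upper bound (every missing ISI taken as insomnia), since the evaluable-only figure is unbiased only if missingness is unrelated to insomnia.
- As a small clarification, state whether one blank ISI item makes the total non-evaluable.

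The cost is SAP wording, with a line in SAP section 4 if the change is regarded as a departure from the protocol's denominator. Both main calculations are already planned, and the upper bound adds one line of output. No new data are needed.

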#### **3.2.2. EQ-5D-5L**

The EQ-5D-5L descriptive system consists of five health dimensions: mobility, self care, usual activities, pain/discomfort and anxiety/depression. Patient's rate each of the dimensions on five levels: no problems, slight problems, moderate problems, severe problems, and extreme problems and these are scored 1 to 5 to give an overall 5-digit health state. For example, state 11111 indicates no problems on any of the 5 dimensions, while state 12345 indicates no problems with mobility, slight problems with washing or dressing, moderate problems with doing usual activities, severe pain or discomfort and extreme anxiety or depression

The EQ-5D-5L also uses a visual analog scale (VAS) where patients rate their health on a vertical scale from 0-100. The data from the VAS can be used as a quantitative measure of health as judged by the individual patients.

For each of the 5 dimensions, data will be reported descriptively as the number and % of patient reporting each level within the 5 dimensions. In addition, a bar chart will also be produced to graphically represent the data.

Statistical Analysis Plan for CLM-INS-004

Version: Final 2.0

Date: 9th September 2022

Data from the VAS will be summarised descriptively as a continuous variable (N, mean, median, min max etc).

The above EQ-5D-5L summaries will also be presented for the Stage 1 analysis set split by those with no insomnia (scores  $\geq 7$ ) versus those with insomnia (score  $\geq 8$ ).

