3.4 Secondary endpoints/outcomes

Secondary evaluation criteria:

- i. Insomnia Severity (ISI): Severity of insomnia will be determined at screening/baseline (all screened patients in Stage 1 of the study) and following the 3-week observational period (all patients enrolled in Stage 2 of the study), based on the total ISI score obtained by summing the seven items to provide a score from 0-28 categorised as follows:
 - 0–7 = No clinically significant insomnia
 - 8–14 = Subthreshold insomnia
 - 15–21 = Clinical insomnia (moderate severity)
 - 22–28 = Clinical insomnia (severe)
- ii. Sleep efficiency (Sleep diary): Participants' responses collected from the sleep diary will be used to calculate sleep efficiency during the observational period: Sleep efficiency = Total sleep time/Total time in bed.
- iii. Quality of Life (EQ-5D-5L): Data from the EQ-5D-5L self-classifier, which includes five dimensions (mobility, self-care, daily activities, pain/discomfort, and anxiety/depression) will be used to calculate an index value as a measure of the participant's health, both at screening/baseline (all screened patients) and following the observational period (all enrolled patients).
- iv. Quality of Life (FACT-ES): Data from the FACT-ES, which includes five subscale domains (physical well-being, social/family well-being, emotional well-being, functional well-being and endocrine symptom subscale), will be used to calculate an index value as a measure of the participant's health, both at screening/baseline (all screened patients) and following the observational period (all enrolled patients).
- v. Compliance of data entry into the digital sleep diary: Compliance will be assessed as the proportion of participants completing the digital sleep diary on at least 17 out of 21 days.
- vi. User Experience Questionnaire (UEQ): Patient experience, feedback, and satisfaction rating from use of digital diary. This will be assessed once (at the end of study), using the UEQ designed to evaluate the participant's experience of the digital sleep diary. Participants who withdraw from the study will be offered the questionnaire.
- vii. Adverse events: The numbers of AEs and serious adverse events (SAEs) will be determined. Participants enrolled in Stage 2 will report AEs at the conclusion of the three-

week observational period in a telephone consultation with the clinical study team. Any relationship with the AE/SAE to the usage of the digital sleep diary will be recorded.

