## 2. ANALYSIS AND REPORTING CONSIDERATIONS

### 2.1. General Considerations

Statistical analysis will be performed using SAS® software. Continuous variables will be summarized using the mean, the standard deviation [SD], median, 25th and 75th percentiles, minimum value, and maximum value. Categorical variables will be summarized using frequency counts and percentages. Data will be listed in data listings.

Where applicable, 95% confidence intervals (CIs) will be presented.

The tables, listing and figures will be developed as a separate standalone document from the SAP. The document will provide templates of the outputs to be provided following database lock based on the summaries detailed in the SAP. All data will be listed, in addition to the summaries outlined in the SAP

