### **3.2.3. FACT-ES**

Quality of Life Data will be reported based on the FACT-ES self-report measure, which includes five subscale domains:

- physical well-being (PWB, 7 items, score of 0-28)
- social/family well-being (SWB, 7 items, score of 0-28)
- emotional well-being (EWB, 6 items, score of 0-24)
- functional well-being (FWB, 7 items, score of 0-28)
- endocrine symptom subscale (ES, 19 items, score of 0-76)

Scores will be derived as follows:

- If  $>50\%$  of items have been answered within a subscale, then multiply the sum of the item scores by the number of items in the subscale, then divide by the number of items answered.
- If  $<50\%$  of items within a subscale have been answered, then the subscale will be reported as NE/missing.

It was discovered during the trial that a single question from the EWB subscale (GE4 “I feel Nervous”) was missing from the questionnaire. This was added in part way through the trial so some patients will not have available data for this specific question. EWB scores will still be derived (as described above) provided at least 50% of the EWB items are available at the time of data reporting.

Note, a higher score reflects a better QoL. Some scores need to be reversed by subtracting the score from 4 (see appendix A for details on reverse scoring for individual items)

Subscales scores as well as an overall FACT-ES total score (total of all 5 subscale scores, PWB+SWB+EWB+FWB)+ES) will be reported for the relevant timepoints. FACT-G scores will also be presented (total of PWB+SWB+EWB+FWB).

Boxplots of the subscale scores and total scores will be presented for each analysis set for the relevant time points.

The above FACT summaries will also be presented for the Stage 1 analysis set split by those with no insomnia (scores  $\geq 7$ ) versus those with insomnia (score  $\geq 8$ ).

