### **3.6. Association of breast cancer characteristics and sleep**

To assess any association with treatment/clinical characteristics and insomnia severity, sleep efficiency and Quality of Life, data will be reported and summarized by the following characteristics for the stage 2 analysis set:

- Breast cancer stage
  - Stage I, II or III
- Treatment regime
  - Systemic, dexamethasone, radiotherapy, hormonal or targeted
- Prior chemotherapy
  - No prior chemotherapy
  - Prior chemotherapy started  $\leq$  3 months of study entry
  - Prior chemotherapy started  $>3$  and  $\leq$  6 months of study entry
  - Prior chemotherapy started  $>$  6 months of study entry
- Baseline insomnia severity
  - subthreshold, moderate, and severe
  - Note no patient should have category of “none” for the baseline assessment since they have to have insomnia to be eligible for Stage 2

The following summary tables will be presented for the above baseline/disease characteristics:

- Insomnia severity at baseline and day 21 (for breast cancer stage, treatment and prior chemotherapy only)
- Sleep efficiency % (average of last 2 weeks)
- EQ-5D-5L, summary of 5 dimensions and VAS at baseline and day 21
- FACT-ES subscale scores, FACT-G and total-ES score at baseline and day 21

In addition to tabular summarises the following plots will be produced

- Bar charts of insomnia severity (for stage, treatment and prior chemotherapy only)
- Line plots of mean daily sleep efficiency (%) over time

Statistical Analysis Plan for CLM-INS-004

Version: Final 2.0

Date: 9th September 2022

- Boxplots of FACT-ES subscale scores, FACT-G and total-ES score at baseline and day 21

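### SAP 3.2.2 and 3.2.3 define the no-insomnia group as ISI ≥ 7; as written, it contains everyone with insomnia and leaves out ISI 0–6

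*SAP*

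**What the plan says.** SAP 3.2.2 describes the EQ-5D-5L tables and then adds a subgroup view of Stage 1 in which the two columns are defined as "no insomnia (scores $\geq 7$ ) versus those with insomnia (score $\geq 8". SAP 3.2.3 does the same for FACT-ES ("The above FACT summaries will also be presented for the Stage 1 analysis set split by those with"), with the same two cut-offs.

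The section just before these sets a different boundary. In SAP 3.2.1, "Insomnia will be defined as a total score of 8 or more", and the lowest severity band is "no clinically significant insomnia (ISI score 0-7"). Protocol 3.4, 6.1, 10.3.3 and Appendix 16.1 all use the same 0–7 band. Protocol 3.4 gives the range of the total: "summing the seven items to provide a score from 0-28".

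Neither the list of protocol changes in SAP section 4 nor the version 2.0 entry in the SAP revision history mentions a new definition of the no-insomnia group. SAP 2.1 says that a separate document will hold "templates of the outputs to be provided following database lock based on the summaries detailed in the SAP".

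**The concern.** The two groups should be mutually exclusive and together cover every participant with an ISI total. The printed rule does neither, because the no-insomnia group (≥ 7) contains the whole insomnia group (≥ 8).

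This is the grouping rule for two sets of tables and plots, and the templates are to be built from the SAP. The sign could therefore pass into the programs, and a check of the outputs against the SAP would not expose it.

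It is also the only place where the SAP compares quality of life between people with and without insomnia. The subgroup summaries in SAP 3.6 are limited to the Stage 2 set, where everyone has ISI ≥ 8 and the baseline severity groups are "subthreshold, moderate, and severe". They cannot supply the comparison if the Stage 1 table is wrong.

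**Working it through.** **Logic check over all possible scores.** The ISI total takes 29 values, 0 to 28.

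| ISI total | No insomnia as printed (≥ 7) | Insomnia (≥ 8) | No insomnia per SAP 3.2.1 (0–7) |
|---|---|---|---|
| 0–6 (7 values) | no | no | yes |
| 7 (1 value) | yes | no | yes |
| 8–28 (21 values) | yes | yes | no |

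As printed, 21 scores are in both groups, 7 are in neither, and only a score of 7 is classified as intended. With ≤ 7 and ≥ 8, no score is shared and all 29 are covered.

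**Planning numbers.** Protocol 10.1 and SAP 1.2.1 give 285 Stage 1 participants and 44% prevalence. 285 × 0.44 = 125.4, which reproduces the plan's 125; 285 − 125 = 160 have no insomnia.

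**Size of the misclassification.** Let f be the share of the 160 who score exactly 7. The documents do not give it, so I take 0–25%. Then n7 = 160 × f, the printed no-insomnia column holds 125 + n7, the share of it with insomnia is 125 / (125 + n7), and 160 − n7 people are left out.

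| f (assumed) | n7 | Column size | With insomnia | Left out |
|---|---|---|---|---|
| 0% | 0 | 125 | 100% | 160 |
| 5% | 8 | 133 | 125/133 = 94% | 152 |
| 12.5% | 20 | 145 | 125/145 = 86% | 140 |
| 25% | 40 | 165 | 125/165 = 76% | 120 |

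**How much of a true mean difference would still show (illustrative).** The printed column's mean is (125 × M + n7 × m7) / (125 + n7), where M is the mean in the insomnia group and m7 the mean among those scoring 7. Its distance from M is therefore n7 / (125 + n7) × (M − m7).

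- If people at ISI 7 have the average quality of life of everyone at 0–7, the fraction still visible is n7 / (125 + n7): 8/133 = 6% at f = 5% and 40/165 = 24% at f = 25%.
- If quality of life is linear in ISI, I assume a mean ISI of 3 among scores 0–6 and of 11 to 16 among scores ≥ 8.
  - Low end (f = 5%, mean 11): the 0–7 mean is (152 × 3 + 8 × 7)/160 = 3.2, so the true gap is 7.8. The visible gap is 8/133 × (11 − 7) = 0.24, and 0.24/7.8 = 3%.
  - High end (f = 25%, mean 16): the 0–7 mean is (120 × 3 + 40 × 7)/160 = 4, so the true gap is 12. The visible gap is 40/165 × (16 − 7) = 2.18, and 2.18/12 = 18%.

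**The case against.** The strongest reply is that this is a self-evident typing error. The correct bands stand in the section immediately before, the group is labelled as having no insomnia, and the sentence calls the comparison a split, so only one reading works. A careful programmer would probably query it. The templates are a separate document that is not available here and may already carry the right sign. I accept all of this: the tables are at risk, not shown to be wrong.

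Second, no stated objective depends on this contrast. The quality-of-life objectives concern patients with ISI ≥ 8, whose column is defined correctly, and the comparison is an additional descriptive view with no test attached. That also stands, and it limits the importance of the point. It does not make the rule right.

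Third, the figures for the visible difference rest on an ISI distribution that the documents do not give. They are scenarios only, and they apply to means (the VAS and FACT scores) rather than to every EQ-5D-5L display. The overlap at 8–28 and the omission of 0–6 need no such assumption.

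Finally, the text was machine-read from PDF, so the sign should be confirmed on the original. A reading error is unlikely: the sign is the same in two sections, and the chemotherapy windows in SAP 3.6 show ≤ correctly.

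**Conclusion.** The concern holds. The no-insomnia definition in SAP 3.2.2 and 3.2.3 is wrong as written and contradicts SAP 3.2.1 and the protocol. It is very probably a slip for ≤ 7, but it is printed twice as the operative rule and nothing corrects it.

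Whatever the ISI distribution, the literal no-insomnia column contains every participant with insomnia and none scoring 0–6. The percentages depend on the planning values of 285 and 44% and on the assumed share at ISI 7.

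The consequence is confined to the descriptive Stage 1 EQ-5D-5L and FACT-ES comparison. The primary prevalence estimate, Stage 2 entry, the sample size and the SAP 3.6 summaries do not use this rule.

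**What to change.** In SAP 3.2.2 and 3.2.3, define no insomnia as an ISI total ≤ 7 and insomnia as an ISI total ≥ 8. Check the output templates, and any programs or tables already built from them, for the same sign.

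State in the same sentences that participants without an evaluable ISI total are shown as missing and placed in neither group. Such participants can occur, because the Stage 1 analysis set in SAP 2.2 requires only one evaluable questionnaire of the three. This agrees with the missing categories already allowed in SAP 2.2 and 3.2.1.

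The cost is one symbol in each of two sentences, a short addition on missing totals, a template check, and the dated SAP version entry with reason that protocol 10.5 requires. I see no statistical drawback.
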